1.2.2 Rationale for selected doses

The LEVALS phase IIa study included treatment periods with 1 mg once a day and 1 mg b.i.d. of levosimendan. These two daily doses of levosimendan showed significant benefits over placebo in supine SVC in a dose-dependent manner. Based on the LEVALS results and studies in cardiac and other patient populations, higher doses are associated with increased HR. Therefore Orion concludes that no further dose finding is needed. The target maintenance dose

DNO 090017ff823c9bac / 1.0 **Approved** 16 / 58

of levosimendan in the phase III study will be 2 mg per day administered as 1 mg b.i.d. Using flexible dosing, the levosimendan arm will start with a 1 mg daily dose for 2 weeks. Previous studies have shown that levosimendan may be associated with headache in a dose-dependent manner, lasting for about 2-3 days. Starting with 1 mg per day will therefore decrease the occurrence of headache. HR has also been shown to increase dose-dependently with levosimendan. If tolerability allows (e.g. based on HR) at 2 weeks, the dose will be increased to 1 mg b.i.d. If required due to any tolerability issues (e.g. based on HR) during 1 mg b.i.d. dosing, the dose can be decreased to 1 mg per day. During b.i.d. dosing the 2nd daily dose will normally be taken at 12 hours, but to best meet the clinical needs of the subject, the investigator may instead specify taking the 2nd daily dose at 6 hours after the morning dose or when the subject goes to bed.

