5.3.2 Dose adjustment

The daily doses of oral levosimendan will be 1-2 mg depending on the tolerability (mainly judged by HR). The subjects will start with a 1 mg dose (in the morning) for 2 weeks.

HR will be assessed in the morning before study drug intake:

- At visit 2 (2 weeks):
 - If the HR in the 12-lead ECG has increased ≤ 15 bpm from baseline, the subject will increase the dose to 1 mg b.i.d.
 - If the HR in the 12-lead ECG has increased > 15 bpm from mean baseline value, the subject will continue with the 1 mg once daily. If the increase in HR is > 30 bpm in 3 separate recordings, the subject must discontinue the study treatment (see section 4.5).

- At visit 3 (4 weeks) or later visits:
 - If the HR in the 12-lead ECG has increased ≤ 20 bpm from baseline, no changes to the dosing regimen are made.
 - If the HR in the 12-lead ECG has increased > 20 bpm from baseline in 3 separate recordings taken within 5-10 minutes from each other, the subject will decrease the dose back to 1 mg once daily if treated with 1 mg b.i.d. In case the increase in HR is > 30 bpm in each of the 3 separate ECG recordings, the HR must be checked again at an additional visit approximately 2 weeks after the dose decrease. If the increase > 30 bpm is recorded at the dose level of 1 mg once daily in 3 separate recordings, the subject must discontinue the study treatment (see section 4.5).

Administration of placebo (1 or 2 capsules per day) will be based on the same criteria as described for levosimendan above.

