6.2.9 Multiple timepoints

The primary efficacy model will include all planned post-baseline visits up to the Week 12 visit. Additional analyses of primary efficacy will include all planned study visits. Included timepoints for other endpoints will be described separately. Baseline measurements of outcome variables will be included as covariates in the models. The MMRM will be used to estimate the covariance between measurements for a given subject, without assuming any specific structure a priori. Planned visit will be included as a factor in the model. For slope analyses, the actual study day of the visit will be used. All time-to-event analyses will be performed up to the first event only.

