7.4 Extent of exposure and treatment compliance

The total number of exposed subjects, the total duration of study treatment exposure (continuous, and categorized both separately and cumulatively at the thresholds of ≤ 4 , ≤ 8 , ≤ 12 , ≤ 24 , and ≤ 48 weeks), and dose levels (in milligrams), averaged over the course of the study as well as at each study visit, will be reported as measures of extent of exposure.

Dose changes will be described by reporting the subject counts in the following categories:

- 1) remained at 1 mg for the entire study (“never increased”)
- 2) uptitrated to 2 mg and remained for the rest of the study (“increased and remained”)
- 3) uptitrated to 2 mg and later downtitrated to 1 mg (“increased, then decreased”).

Dose changes will also be reported by acetylation status.

Treatment compliance will be described by reporting the number of dispensed and returned study treatment capsules at each study visit. The number of subjects with treatment interruptions longer than 7 days will be reported with descriptive statistics.

Both extent of exposure and treatment compliance will be tabulated with descriptive statistics.

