7.9.2 Adverse events

Adverse events (AEs) will be classified by system organ classes (SOC) and preferred terms (PTs) using the MedDRA dictionary version 23.0.

A treatment-emergent AE (TEAE) is defined as any event arising or worsening after the start of study drug administration until 25 days after the last study medication intake.

A summary of TEAEs and non-TEAEs will be presented, showing total numbers of events and subjects having events:

1. Fatal outcome
2. SAE status
3. Other significant AEs
4. AESI status
5. Causality
6. Severity

7. Actions taken

The number of TEAEs, and number and proportion (%) of subjects having TEAEs by SOC and PT will be given by treatment group. The number of events will also be broken down by:

1. Severity (mild, moderate, severe)
2. Causality (related, not related)
3. Timing with respect to starting treatment (disjoint union of: ≤ 2 weeks, ≤ 4 weeks, ≤ 8 weeks, ≤ 12 weeks, ≤ 24 weeks, ≤ 48 weeks)
4. Tertiles of OR-1896 concentration at the Week 4 visit (total of 4 groups: None, and others classified into Low, Medium, and High according to observed tertiles)
5. Dose change groups (see 7.4)

Incidence rates for first events adjusted for exposure time will also be reported. They are calculated by dividing the number of subjects ever experiencing the event while on treatment by the number of days subjects were exposed to the study treatment.

All serious adverse events (SAEs) and other significant AEs will be evaluated case by case. Narrative descriptions will be included in the study report for all AEs leading to death, other SAEs, AEs leading to study treatment withdrawal, and certain other significant AEs (OSAEs).

Groups of treatment emergent AEs of special interest (AESIs) are defined by Standardized MedDRA Queries (SMQs) where noted, and by in-house search categories (IHSCs) defined as lists of preferred terms, otherwise. Statistics for the following AESIs will be reported:

1. Decrease in red cell parameters
2. Drug related hepatic disorders - comprehensive search (SMQ)
3. Haemorrhages (SMQ)
4. Headache
5. Hypokalaemia (SMQ)
6. Hypotension
7. Increased heart rate
8. Ischaemic heart disease (SMQ)
9. Neurocognitive disorder
10. Palpitations
11. Suicide/self-injury (SMQ)
12. Supraventricular tachyarrhythmias (SMQ)
13. Ventricular tachyarrhythmias (SMQ)

See Appendix 10.2 for the queries used to create the groups. If an SMQ has both a broad and a narrow definition, the narrow search will be used.

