In addition to standard AE reporting, detailed characteristics will be reported for AESIs:

1. SAE status
2. Need for concomitant medications
3. Severity
4. Changes in dosage
5. Outcome
6. Timing with respect to starting treatment

7. Duration of event
8. Safety subgroups (listed in 6.2.14)

Further, for AESIs, 95% confidence intervals (CIs) will be reported for incidence proportions and incidence rates, and risk ratios and incidence rate ratios (with 95% CIs) between the treatment groups will be estimated.

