7.11 Changes from the clinical study protocol

Specification of the statistical model used in the primary efficacy analysis has been clarified.

All references to "treatment arm" have been changed to "treatment group" instead, to be consistent with the terminology used in the study's title.

Statistical hypotheses have been reworded to match model parameters. The core of the content remains unchanged.

Changed wording in the "data sets to be analysed" section to refer to "important protocol deviations" rather than "relevant major protocol deviations" when talking about the per-protocol

population. This change was made to be consistent with terminology across study communication. The core meaning remains unchanged.

Per-protocol analyses will be conducted in two separate PP populations, depending on the endpoint: PP up to week 12, and PP up to week 48. As key endpoints are assessed at different time points during the study, this provides better control for excluding subjects with deviations that could have affected the efficacy analyses.

Expanded interim analysis section to cover recommendation process in more detail.

Unacceptable quality SVC measurements will be excluded from the primary analysis.

Additional endpoints:

1. Time to any assistive device
2. Time to any respiratory assistive device
3. Time to continuous use of NIV during the night
4. Time to continuous use of NIV during the day and night
5. Time to tracheostomy, continuous ventilator dependence, or death

Additional analyses:

1. King's clinical stage will be estimated from the ALSFRS-R.
2. Restricted mean survival time will be described for time-to-event endpoints.
3. Dose change profiles will be described.
4. Correlations for biomarkers will be described, in a separate report.
5. Concentration-effect plots will be shown for SVC and QTc vs. OR-1896.
6. Adverse events will be reported by timing with respect to starting treatment, OR-1896 concentration at the Week 4 visit, and dose change profile.
7. Incidence rates will be reported for AEs.
8. Groups of TEAEs of special interest will be reported.
9. Confidence intervals for incidence proportions, incidence rates, risk ratios and incidence rate ratios will be reported for AESIs.
10. Narrative descriptions will be written for deaths, TESAEs and other significant TEAEs.
11. AEs will be reported in safety subgroups.
12. Many new categorical analyses for laboratory results will be included.

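### SAP 7.9.2 names its adverse event rate a first-event incidence rate, but the formula keeps counting a subject's treatment days after the first event

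*SAP*

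**What the plan says.** SAP 7.9.2 announces the measure thus: "Incidence rates for first events adjusted for exposure time will also be reported". The next sentence gives the calculation: "dividing the number of subjects ever experiencing the event while on treatment by the number of days subjects were exposed to the study treatment". For adverse events of special interest (AESIs), the same section adds 95% confidence intervals for incidence proportions and rates, and states that "risk ratios and incidence rate ratios (with 95% CIs) between the treatment groups will be estimated".

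Three other places bear on the denominator:

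- SAP 7.4 lists the exposure measures. The only one that measures time on treatment is "the total duration of study treatment exposure".
- SAP 6.2.9 states "All time-to-event analyses will be performed up to the first event only". That rule is written for time-to-event analyses, and 7.9.2 neither refers to it nor repeats it.
- SAP 7.11 records the addition to the protocol only as "Incidence rates will be reported for AEs".

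**The concern.** In a first-event rate, a subject contributes time until the first event or the end of exposure, whichever comes first. The formula in 7.9.2 applies the first-event rule to the numerator only. Followed as written, affected subjects add days during which they can no longer contribute an event.

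Staying on treatment after an event is realistic here, including for AESIs. Protocol 1.2.2 says "levosimendan may be associated with headache in a dose-dependent manner, lasting for about 2-3 days", and headache is not among the mandatory reasons for stopping in Protocol 4.5. Under Protocol 5.3.2, a confirmed heart rate rise above 20 bpm from visit 3 onwards means that "the subject will decrease the dose back to 1 mg once daily if treated with 1 mg b.i.d", so treatment continues. Protocol 1.3.2 names headache, increased heart rate and palpitations as the most commonly reported adverse drug reactions, and common events are where the formula matters most.

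At stake are the reported rates and the AESI rate ratios with their intervals. A reader would take a figure for subjects per total exposure as a first-event rate. If exposure is similar in the two arms, the rate ratio also largely repeats the risk ratio promised in the same sentence.

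**Working it through.** The documents state no adverse event rate, so there is no plan figure to reproduce.

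**1. Direction (no assumptions).** Let x be the number of affected subjects, C the days on treatment for each subject, and T the day of first event.

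- SAP rate = x / sum(C)
- First-event rate = x / sum(min(T, C))

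Because min(T, C) ≤ C, the SAP rate is at most the first-event rate. It is strictly lower once any affected subject continues treatment, and the two are equal only if every affected subject stops at the event.

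**2. Inputs for size.** From the documents: 48 weeks of treatment (Protocol 5.3.1), so 336 days or 336/365.25 = 0.920 years; about 300 levosimendan and 150 placebo subjects (SAP 5). Assumed: event rates, onset days, full exposure in both arms and, unless stated otherwise, affected subjects continuing.

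**3. Constant hazard.** With true rate λ and t = 0.920 years, the SAP formula gives (1 − exp(−λt))/t.

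| True rate per 100 PY | SAP formula | Understated by |
|---|---|---|
| 5 | 4.89 | 2.3% |
| 10 | 9.55 | 4.5% |
| 20 | 18.27 | 8.7% |
| 40 | 33.47 | 16.3% |

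**4. Ratio when the true value is 2.0.** Expected events are 300 or 150 times (1 − exp(−λt)), and SE(log ratio) = sqrt(1/events_active + 1/events_placebo). The shift is ln(2/ratio) / (1.96 × SE), as a share of the half-width of the 95% CI on the log scale.

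| True rates per 100 PY | SAP ratio | 95% CI | Shift |
|---|---|---|---|
| 5 v 2.5 | 1.977 | 0.60–6.49 | 1.0% |
| 10 v 5 | 1.955 | 0.84–4.56 | 2.7% |
| 20 v 10 | 1.912 | 1.04–3.51 | 7.4% |
| 40 v 20 | 1.832 | 1.18–2.85 | 19.9% |

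**5. The shift can go the other way.**

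- Different timing: 20% affected at day 300 against 18% at day 7. SAP ratio = 0.20/0.18 = 1.11. First-event ratio = [0.20/(0.80×336 + 0.20×300)] / [0.18/(0.82×336 + 0.18×7)] = (0.20/328.8)/(0.18/276.78) = 0.94.
- Stopping in one arm only: true rates 40 v 20, with all affected subjects stopping at the event in the active arm and continuing on placebo. SAP ratio = 40/18.27 = 2.19, against 2.0.

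**6. Early onset.** Let a share p be affected at week o, all continuing to week 48. The first-event rate is p/((1 − p)×48 + p×o). For 30% v 15% and o between 1 and 4 weeks:

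- SAP rates are understated by 29.4% to 27.5% in the active arm and 14.7% to 13.8% on placebo.
- The ratio is 2.00 by the SAP formula and 2.42 to 2.38 with days ended at the first event.
- The ratio under proportional hazards is ln(0.70)/ln(0.85) = 2.19.

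For early-clustered events, neither average rate reproduces the hazard ratio.

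**The case against.** Subjects with an event per total exposure is a legitimate safety measure. The label can be read to fit it, with first events describing the numerator and exposure adjustment the denominator, and the formula is printed in full, so nothing is hidden. All sizes above rest on assumed frequencies and onset days, and the effect on the ratio is slight except for common events. The reversal examples use constructed inputs. For increased heart rate the gap may be narrower, because Protocol 1.1 reports that it led to discontinuations in LEVALS and Protocol 4.5 requires stopping for a confirmed rise above 30 bpm on 1 mg once daily. For early events the at-risk ratio is about as far from the proportional-hazards ratio as the SAP ratio is: on the log scale ln(2.19/2.00) = 0.09, against ln(2.38/2.19) = 0.08 to ln(2.42/2.19) = 0.10. Timing breakdowns, proportions and risk ratios are reported as well.

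Most of this stands, and it limits the point to a minor one. It does not remove it. Reading the label as describing the numerator alone does not turn the result into a first-event rate, and 7.9.2 nowhere tells the reader that days after the event are counted. The reversal examples show only that the direction of the shift in the ratio is not guaranteed; they do not predict a misleading result in this trial.

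**Conclusion.** The concern holds, at minor severity. The formula in SAP 7.9.2 does not produce the quantity that the section names. That the rate is never above the first-event rate, and is below it when affected subjects continue treatment, follows from the definitions alone. The size is assumption-based: about 2% to 16% understatement for true rates of 5 to 40 per 100 patient-years under constant hazards, and 27% to 29% for an event that affects 30% of subjects in weeks 1 to 4. The AESI rate ratio is pulled toward 1 only if event timing and stopping after the event are similar in both arms. The effect is negligible for rare AESIs and nil where the event ends treatment in every affected subject. Incidence proportions, risk ratios, timing tables and efficacy analyses are unaffected, and no hypothesis test or stopping rule uses the rate.

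**What to change.** Either of two changes to SAP 7.9.2 settles the point.

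1. **Match the formula to the name.** For each event term, define the denominator as days from first dose to the first on-treatment occurrence for affected subjects, and all days of exposure for the others. Use it for the incidence rates, the rate ratios and their 95% CIs. Add that for early-clustered events this averages a changing hazard, so its ratio can exceed a proportional-hazards ratio and should be read with the timing breakdown.
2. **Match the name to the formula.** Keep total exposure, call the measure *subjects with event per total exposure time*, and say that its ratio approximates the risk ratio when exposure is similar in the two arms.

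The first costs one definition, the added caution and a small programming change that uses adverse event onset dates. The at-risk rate will still average over any change in hazard. The second costs wording only.

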7.9.3 Laboratory values

Protocol-specified laboratory safety variables will be evaluated using descriptive statistics, line plots, and shift plots, showing the baseline value and post baseline values up to the end of treatment. Frequencies of normal and abnormal (low and high) laboratory findings will be summarised based on reference ranges provided for each analyte, and clinical significance of the findings will be evaluated.

Results from additional laboratory variables that were not specified in the protocol will not be summarised, but will appear in patient data listings.

A listing of patients fulfilling Hy's law criteria will be provided. That is, patients meeting all of the following criteria at a given visit:

1. Aspartate or alanine transaminase (AST, ALT) $\geq 3x$ the upper limit of normal (ULN)
2. Serum alkaline phosphatase $< 2x$ ULN
3. Bilirubin $\geq 2x$ ULN

Ratios of AST and ALT to ULN will be plotted against ratios of bilirubin to ULN for all subject-visits. Comparisons of both AST and ALT to the thresholds of $> 2, 3, 5,$ and 10 times their respective ULN will be summarised.

Renal impairment status will be determined from creatinine clearance (eGFR) (NICE) (Unwin et. al, 2011):

- Normal: ≥ 90 mL/min
- Mild reduction: 60 to 89 mL/min
- Mild to moderate reduction: 45 to 59 mL/min
- Moderate to severe reduction: 30 to 44 mL/min
- Severe reduction: 15 to 29 mL/min
- Kidney failure / End stage renal disease: < 15 mL/min

Hepatic impairment status will be determined as:

- Normal: Total bilirubin and AST \leq ULN
- Mild hepatic impairment: Total bilirubin $>$ ULN to $1.5 x$ ULN or (Total bilirubin \leq ULN and AST $>$ ULN)
- Moderate impairment: Total bilirubin $>$ 1.5 to $3 x$ ULN, any AST
- Severe impairment: Total bilirubin $>$ $3 x$ ULN, any AST

Additionally, descriptive statistics of the following categorised analytes will be reported:

Renal impairment thresholds based on creatinine levels in the blood (CTCAE v5.0):

- Grade 1: > ULN–1.5 x ULN
- Grade 2: > 1.5–3.0 x baseline or > 1.5–3.0 x ULN
- Grade 3: > 3.0 x baseline or > 3.0–6.0 xULN
- Grade 4: > 6.0 x ULN

Low potassium levels (hypokalemia) in blood (Unwin et al, 2011; Castro, 2019):

- Mild: 3 to 3.4 mmol/L
- Moderate: 2.5 to < 3 mmol/L
- Severe: < 2.5 mmol/L

Haemoglobin levels in blood (WHO, 2011):

- Non-pregnant women:
 - Mild: 110–119 g/L
 - Moderate: 80–109 g/L
 - Severe: < 80 g/L
- Pregnant women:
 - Mild: 100–109 g/L
 - Moderate: 70–99 g/L
 - Severe: < 70 g/L
- Men:
 - Mild: 110–129 g/L
 - Moderate: 80–109 g/L
 - Severe: < 80 g/L

Haematocrit levels in blood (Cohen et al, 2017):

- Women:
 - Low: < 37%
 - High: > 47%
 - Normal: 37% to 47%
- Men:
 - Low: < 42%
 - High: > 52%
 - Normal: 42% to 52%

Erythrocytes count in blood (Dean, 2005):

- Women:
 - Low: < $3.5 \times 10^{12}/L$
 - High: > $5.5 \times 10^{12}/L$
 - Normal: $3.5\text{--}5.5 \times 10^{12}/L$
- Men:
 - Low: < $4.3 \times 10^{12}/L$
 - High: > $5.9 \times 10^{12}/L$
 - Normal: $4.3\text{--}5.9 \times 10^{12}/L$

7.9.4 12-lead ECG

Descriptive statistics of standard 12-lead ECG variables and abnormal ECG findings will be tabulated by treatment group for each study visit.

QT values will be corrected (QTc) according to Bazett's (QTcB) and Fridericia's (QTcF) formulae. Disjoint comparisons of QTc values to the following thresholds will be summarised:

1. Absolute values > 450 ms, > 480 ms, and > 500 ms.
2. Changes from baseline > 30 ms, and > 60 ms.

Cardiac safety will be assessed by modelling the dose-response of post-dose OR-1896 concentration vs. $\Delta\Delta\text{QTcF}$ at each visit with PK samples. $\Delta\Delta\text{QTcF}$ is defined as the difference between change from baseline between placebo and treatment, where the placebo effect is estimated for each visit with an ANOVA model.

Disjoint comparisons of Masterscope heart rate (EGHRMS) changes from baseline to the protocol-defined thresholds of > 20 bpm and > 30 bpm will be summarised by treatment group, visit, and dose level at the visit.

For subjects whose dose-level is increased at Week 2, changes in Masterscope heart rate between the measurements taken before dosing at the Week 2 and Week 4 visits will be described.

For subjects whose dose-level is reduced, changes in Masterscope heart rate between the last measurement on the higher dose and the following measurement on the lower dose will be described.

The correlation between OR-1896 concentration and post-dose Overread heart rate (EGHROR) will be described with semi-log scatterplots at each study visit.

Drug-drug interactions with medications known to affect QT interval (see 7.10.1) will be evaluated for QT, QTcF and QTcB with descriptive statistics.

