4.5 Removal of subjects from treatment or assessment

Study subjects are free to discontinue the study at any time without providing a reason. However, the investigator should try to identify the reason and document it in the CRF.

A subject must discontinue the study treatment for the following reasons:

- HR increase of > 30 bpm from baseline (visit 1) at the dose level of 1 mg once daily in 3 separate ECG recordings, taken within 5-10 minutes from each other before the morning dose of the study drug (see also section 6.5.4).
- Life-threatening supraventricular or ventricular arrhythmia.
- The investigator judges that it is in the best interest of the subject to stop the study treatment due to any other abnormality compromising patient safety. However, the investigator should consult the medical monitor whenever possible in these instances.
- Pregnancy.
- Invasive mechanical ventilation by intubation or tracheostomy.

The subjects who have discontinued the study medication, but continue in the study, are encouraged to follow the study visit and phone call schedule according to the study protocol for recording ALSFRS-R, ventilatory support and survival status. End-of-study visit assessments for these subjects will be performed 14-25 d after the last study treatment administration.

A subject must discontinue the study if the investigator or the sponsor considers the discontinuation to be medically necessary or in the best interest of the subject.

Irrespective of the reason for discontinuation, the subject should be invited to end-of-study assessments as soon as possible. As long as the subject consents, all relevant assessments, at least those of safety, should be performed, preferably according to the schedule for the end-of-study assessments.

The study monitor should be notified about premature discontinuations by email/phone/fax within 24 hours in the event of discontinuation due to an SAE (see section 6.5.1.3) or within 7 days in the event of discontinuation due to another reason.

DNO 090017ff823c9bac / 1.0 Approved 22 / 58

Subjects who prematurely discontinue will not be replaced. Discontinued subjects are not allowed to re-enter the study.

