Also for subjects who discontinue treatment but continue in the study, end-of-study visit assessments will be performed 14-25 d after the last study treatment administration

² 3 baseline recordings pre-dose

³ Except thyroid-stimulating hormone (TSH)

⁴ Data requested for the past 7 days prior to baseline visit

⁵One sample during the study preferably at visit 1 (baseline)

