6.1.5 Procedures during the post-treatment period

An end-of-study visit will take place 14-25 days after the last study treatment administration for each subject. The following procedures will be performed:

- HR and BP will be recorded.
- 12-lead ECG will be recorded.
- SVC supine will be assessed.
- The Borg CR10 scale to assess the intensity of dyspnoea will be completed at rest in sitting and supine positions (immediately before SVC measurement).
- Physical examination will be performed.
- Weight will be recorded.
- A blood sample for haematology and clinical chemistry and a urine sample for urinalysis will be collected. A pregnancy test will be performed for females of childbearing potential.
- AEs, current medical conditions and concomitant treatments will be recorded.
- Status for NIV support, invasive mechanical ventilation by intubation or tracheostomy and survival will be recorded
- Suicidality will be assessed.

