6.1.6 Follow-up period for subjects who have discontinued the study medication

The subjects who have discontinued the study medication, but continue in the study, are encouraged to follow the study visit and phone call schedule according to the study protocol for recording ALSFRS-R, ventilatory support and survival status.

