6.5.6 Laboratory safety assessments

The following laboratory tests will be taken at the screening visit after at least 10 hours of fasting:

Haematology:

- Haemoglobin
- Haematocrit
- Erythrocyte count
- Leukocyte count
- Platelet count
- Differential count (lymphocytes, monocytes, eosinophils, neutrophils, basophiles)
- Mean corpuscular volume

Mean corpuscular haemoglobin

Chemistry:

- Albumin
- Alkaline phosphatase (ALP)
- Bilirubin total
- Bilirubin conjugated
- Calcium
- Creatine kinase
- Creatinine
- Creatinine clearance
- C-reactive protein
- Gamma-glutamyl transferase (GGT)
- Alanine aminotransferase (ALT)
- Aspartate aminotransferase (AST)
- Glucose
- Lactate dehydrogenase
- Potassium
- Sodium
- Troponin T
- TSH

Urinalysis:

- Glucose
- Protein
- Erythrocytes
- Leucocytes

Serology:

- Hepatitis B surface antigen (HBsAg)
- Hepatitis C virus antibody (HCVAb)

Haematology, chemistry (except TSH) and urinalysis will be repeated at each visit during the treatment period and at the end-of-study visit.

A pregnancy test for female subjects of childbearing potential will be performed at screening and baseline and at each visit during the treatment period (except visit 2, i.e. 2 weeks after baseline) and at the end-of-study visit.

The investigator will review all laboratory results and assess them for clinical significance. In case there are abnormal findings, control assessments can be performed according to the judgement of the investigator.

Instructions for the collection, handling, storage and transportation of samples will be provided before the start of the study.

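### SAP 7.9.3 ends the laboratory descriptive statistics, line plots and shift plots at end of treatment, so the scheduled off-drug end-of-study sample does not appear in these three displays

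*SAP*

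**What the plan says.** **The limit.** The first sentence of SAP 7.9.3 presents the laboratory variables as descriptive statistics, "line plots, and shift plots, showing the baseline value and post baseline values up to the end of treatment". The section does not define end of treatment.

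**What is collected.** Protocol 6.5.6: "Haematology, chemistry (except TSH) and urinalysis will be repeated at each visit during the treatment period and at the end-of-study visit". (Table 1 omits urinalysis at visits 2 and 4.) Protocol 6.1.5, under the post-treatment period: "An end-of-study visit will take place 14-25 days after the last study treatment administration for each subject", and at that visit "A blood sample for haematology and clinical chemistry and a urine sample for urinalysis will be collected".

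**Subjects who stop early.** A footnote to Table 1 in protocol 6.1 covers those who stop treatment but stay in the study: "end-of-study visit assessments will be performed 14-25 d after the last study treatment administration". Protocol 6.1.6 says they are "encouraged to follow the study visit and phone call schedule according to the study protocol for recording ALSFRS-R, ventilatory support and survival status"; no laboratory test is named. Protocol 4.5 adds that, whatever the reason for discontinuation, "the subject should be invited to end-of-study assessments as soon as possible", preferably on the end-of-study schedule.

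**Adverse events.** SAP 7.9.2 counts an event as treatment-emergent "until 25 days after the last study medication intake".

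**The concern.** A safety sample scheduled for every subject is left out of the three displays that open the laboratory section. Protocol 8.4.8.3 makes descriptive statistics and line plots the primary laboratory evaluation and sets no such cut-off. SAP 7.11 drops the optional laboratory MMRM, so these displays carry more of the weight.

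Two things are lost from them:

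- **Persistence or reversal off drug.** Protocol 1.3.2 reports small falls in red-cell measures and serum potassium in some studies, and SAP 7.9.2 makes both topics adverse events of special interest. A comparison of the last on-treatment value with the off-drug value would show whether such falls resolve.
- **The only later scheduled sample after a between-visit stop.** For a subject who stops drug between visits, nothing after the previous visit appears in these displays.

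**Working it through.** The plan gives no figure to reproduce. The check sets the SAP's time windows side by side and then does schedule arithmetic.

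**Step 1. Time windows in the same SAP**

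| Data | Where | Window |
|---|---|---|
| Laboratory descriptive statistics, line plots, shift plots | 7.9.3, first sentence | Up to end of treatment |
| Abnormality frequencies, transaminase thresholds, categorised analytes | 7.9.3 | None stated |
| Hy's law listing; AST/ALT-bilirubin plot | 7.9.3 | Any visit; all subject-visits |
| ECG; vital signs | 7.9.4; 7.9.5 | Each study visit |
| Treatment-emergent adverse events | 7.9.2 | To 25 days after last intake |
| Supine SVC | 7.5.1.1 | Change from last on-treatment value to end-of-study described |

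Only the first row stops at end of treatment. The list of changes in SAP 7.11 covers new laboratory categories and the dropped MMRM, but not this cut-off.

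**Step 2. Gaps between scheduled laboratory visits**

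The study days in protocol Table 1 are 1, 15, 29, 57, 85, 169, 253 and 337. Successive differences are 14, 14, 28, 28, 84, 84 and 84 days, in total 336. The share of treatment time lying in 12-week gaps is (84 + 84 + 84)/336 = 252/336 = 75%.

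Ignoring visit windows, a subject who stops between two visits after Week 12 can have up to 84 − 1 = 83 days of exposure after the last scheduled on-treatment sample. If stops are uniform within the gap (an assumption), the average is 84/2 = 42 days. If stops are uniform over all 48 weeks (also an assumption), the average is the sum of gap²/2 divided by 48:

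(4 + 4 + 16 + 16 + 144 + 144 + 144)/2 ÷ 48 = 236/48 = 4.9 weeks.

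In the longest case, the next scheduled sample is the end-of-study one, 83 + 14 = 97 to 83 + 25 = 108 days after the previous one.

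**Step 3. What the end-of-study sample measures**

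Protocol 1.1 gives a half-life of 60 hours for the active metabolites, in healthy subjects. It is assumed here to apply to ALS patients. The remaining fraction is 0.5^(days × 24/60).

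- Day 14: 14 × 24/60 = 5.6 half-lives; 0.5^5.6 = 0.021, about 2.1%.
- Day 25: 25 × 24/60 = 10 half-lives; 0.5^10 = 0.001, about 0.1%.

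The sample is in effect taken off drug. It can show a persisting or delayed change, or recovery. It cannot stand in for the on-drug values missed in Step 2.

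**The case against.** **Limiting by-visit displays to on-treatment values is a legitimate choice.** It keeps the displays interpretable as on-drug data. This stands as an argument against merging off-drug values into them, but not against a separate, labelled time point.

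**The rest of 7.9.3 has no stated cut-off.** This is correct. A reader might infer that end-of-study results vanish from the whole laboratory analysis, but the documents do not say so. The creatinine, potassium, haemoglobin, haematocrit and erythrocyte categories may include them, as may the liver displays. The limiting phrase could even be read as attaching to the plots alone. The omission is established, on the plain reading, for three displays only.

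**Important abnormalities are caught elsewhere.** Protocol 6.5.1.1 makes a clinically significant laboratory change an adverse event, and the treatment-emergent window reaches the end-of-study visit. Red-cell decrease, hypokalaemia and hepatic disorders are events of special interest, and AEs leading to treatment withdrawal get narratives. This lowers the stakes. It does not give the average or individual change off drug, and not every abnormal value becomes an adverse event.

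**A reader might infer that the end-of-study sample covers an early stopper's last weeks of exposure.** Step 3 shows that it does not when taken on schedule. The request in protocol 4.5 for prompt assessment could bring some samples forward, but the same sentence prefers the end-of-study schedule, and the 14-25 day rule is explicit for those who stay in the study.

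**A reader might want a count of affected subjects.** The documents do not supply one. The dropout allowance of about 20% belongs to the sample size for the 12-week SVC comparison and is not a 48-week rate of stopping drug. Subjects stopped at a scheduled visit, for example under the heart-rate rule, have samples scheduled that day, and some stoppers will have no end-of-study sample.

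**Conclusion.** The point holds for the descriptive statistics, line plots and shift plots. On its plain reading, SAP 7.9.3 leaves a scheduled safety sample out of them, in contrast to how the SAP treats ECG, vital signs, adverse events and SVC, and without declaring a change from the protocol. What these displays lose is the view of persistence or reversal off drug, and the only later scheduled sample for subjects who stop between visits.

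Severity is minor. These are descriptive safety displays, the samples are collected anyway, and no efficacy conclusion depends on them. The conclusion rests on reading end of treatment as the last dose, since the end-of-study visit sits in the protocol's post-treatment period. The 42-day and 4.9-week averages rest on uniform stop times and only illustrate the spacing of visits. The residual-drug figures rest on the healthy-subject half-life.

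**What to change.** In SAP 7.9.3:

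1. Define end of treatment and state the time window for each laboratory display, including those that now have none.
2. Show the end-of-study value as a separate time point, labelled post-treatment, in the descriptive statistics and line plots.
3. Describe by treatment group the change from the last on-treatment value to the end-of-study value for haemoglobin, haematocrit, erythrocytes and potassium, as SAP 7.5.1.1 already does for SVC.
4. Keep the shift plots on-treatment, or mark end-of-study values in them as off-drug. Do not use the end-of-study value as the final value for early stoppers: that would set off-drug values for them beside on-drug values for completers and could hide reversible effects.
5. Record the choice in SAP 7.11.

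The cost is a few sentences, one extra column per laboratory table and one short table for four analytes. No new data are needed. Where an end-of-study visit was held remotely, protocol 6.6 accepts local laboratory panels, so the change table should flag or separate local results.
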